5.1 Methodology and methods

A mixed methods approach will be used throughout this hospital-based feasibility study designed in accordance with MRC framework for Developing and evaluating complex interventions (MRC 2008). The pragmatic paradigm, which has gained increasing popularity amongst healthcare researchers in recent years, will inform research design for this study. This approach, often termed the 'third way' emerged in response to the inherent limitations of traditional paradigms, including post-positivism and constructivism, in fully addressing multifaceted research questions (Tashakkaori and Teddlie 1998). The pragmatic approach has intuitive appeal for health-care research as rigid adherence to any particular

philosophical stance is rejected and the emphasis is placed on the research question and how best to address it (Armitage 2007). Methods of data collection and analysis are selected according to the likelihood of providing insight into the question (Creswell 2003). Pragmatism underpins the use of mixed methods research, accepting qualitative and quantitative methods either in parallel or sequential stages (Tashakkaori and Teddlie 1998, Creswell 2003). Advocates of mixed-methods research argue that this integration of approaches enhances the quality of many studies, increasing the breadth and depth of enquiry into complex social phenomena (Tashakkaori and Teddlie 1998).

For a full-scale evaluation, individual randomisation would be undesirable due to the risk of contamination between the trial arms and the organisational-level changes required by the intervention. A stepped-wedge (one-way crossover) design in which the intervention is rolled out in phases, the order determined at random but all clusters receiving the intervention by the end of the trial, is currently considered as the most appropriate design. For feasibility, a pre and post-cohort design, over 12 months, will be conducted to allow implementation of the intervention in the study site and assessment of the feasibility of a stepped wedge approach.

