5.2 Setting

The study will take place in a health facility in the metropolitan province of Bulawayo in Zimbabwe. MPilo Central Hospital is the largest hospital in Bulawayo, and second largest in Zimbabwe after Parirenyatwa Hospital in Harare. Mpilo is a public hospital and referral centre for the Matabeleland North, Matabeleland South and Midlands provinces of Zimbabwe. Births per year exceed 9,000. The hospital is a teaching hospital for obstetric care providers and centres for research and specialised care. Data from our recently performed cross-sectional study (UREC Ref 2018-4429-6165), confirms women in a subsequent pregnancy following stillbirth book for antenatal care between 18-35 weeks gestation (median 26 weeks).

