5.4.1 Phase 1: (Pre-implementation - control phase; months 1-7)

Women recruited during the control phase will have existing care provided for women with subsequent pregnancies following stillbirth. There is no current defined pathway for care in pregnancy following stillbirth. The control phase of the study will provide clearer

understanding of usual care in the study site; refine content and delivery of the intervention and pilot data collection tools for the subsequent trial.

- A group comprising of women having the current standard of antenatal care at the study site will be recruited as controls to explore experiences of standard antenatal care, worries in pregnancy and perceptions of preparation for childbirth by completing questionnaires at the beginning and towards the end of their pregnancy (study months 1-7 of Phase 1).
- A sub-sample of women will also be invited to attend focus group interviews or individual interviews, whichever they prefer, at the end of their pregnancy to capture pregnancy experiences, including impacts of the intervention (study months 1-7 of Phase 1).
- Health workers (midwives, nurses, obstetricians, and support staff), and other hospital staff, including managers and administrators, will be invited to attend focus group interviews to contribute to refinement of the intervention and identify areas requiring a change of practice in the existing antenatal clinic area. The focus group interviews will identify the needs for education and training of staff and establishing care pathways for women attending the study site in a subsequent pregnancy following stillbirth (study month 1).
- Specialist antenatal clinical care staff will be identified to run the specialist clinic and provide psychosocial support and delivery of birth preparation information needs to the women in Phase 2 an obstetrician and two midwives and one support worker with an interest in this topic will be required (study month 2).
- Specialist antenatal clinical care staff will attend a training workshop (content based on existing educational resources, to be refined during Phase 1) to introduce the intervention, raise awareness of women's needs and identify areas requiring a change of practice in the existing antenatal clinic area (study month 2).
- Health workers (midwives, nurses, obstetricians, and support staff), and other hospital staff, including managers and administrators, directly involved in the

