- intervention will be asked to compete a staff experience questionnaire at the end of Phase 1 (study month 12).
- The proposed intervention has been informed by exploratory work from NIHR Global Health Research Group on Stillbirth Prevention and Management in Sub-Saharan Africa, and the Lugina Africa Midwives' Research Network (lamrn.org). The local Zimbabwe stillbirth Community Involvement and Engagement group, local women who have experienced a stillbirth, will be asked to contribute to the refinement and implementation of the proposed antenatal clinical service (July/August 2019).

5.4.2 Phase 2: (Specialised antenatal clinical care with psychosocial support and preparation for birth – intervention phase); months 4-12)

The proposed specialised antenatal clinical service will be designed to improve the quality of antenatal care provision, reduce the risk of pregnancy complications, including stillbirth and give women a positive pregnancy experience. The clinic will comprise two major components: specialised antenatal clinical care and psychosocial support and preparation for birth. Women will be considered high risk, have continuity of carer, an individualised structured care plan and regular antenatal appointments. The clinic will adhere to guidelines set out by WHO Recommendations on antenatal care for a positive pregnancy experience (WHO 2016). A psychosocial support and preparation for birth programme will be developed to enhance women's pregnancy experience and help women approach birth positively. The programme will comprise specialist antenatal classes for women including preparation for birth, and recognising and managing worry. Women will be offered the opportunity to build relationships with other women to enhance social support during pregnancy. The precise content and delivery of the programme will be finalised during this phase.

The intervention will be implemented in the study site in month 4.

- The specialised antenatal clinic will be launched at the study site. The specialist antenatal clinical care staff will initiate this with support from a research team facilitator, research assistants/midwives, and hospital staff including managers and administrators (study month 4).
- Specialist antenatal care, including psychosocial support and a preparation for birth programme will be delivered by the specialist antenatal clinical care staff, with support from the research team facilitator (study months 4-12).

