Individual consent will not be sought for attendance at either the current antenatal clinic (control phase 1) or the proposed specialised antenatal clinic (intervention phase 2), as both are considered standard practice. The current antenatal clinic running throughout Phase 1 will be superseded with the specialised antenatal clinic in Phase 2 of the study period. Both will be provided for all women attending antenatal services at the study site who have experienced a previous stillbirth, irrespective of their participation in the study / questionnaire completion / focus group / individual interview participation.

Consent will be sought for data collection associated with the assessment of the feasibility of a full-scale trial, acceptability and uptake of the intervention for women and facility staff. Identification of women with a history of stillbirth will be undertaken by appropriately trained and experienced members of the clinical team and confirmation of eligibility and consenting of participants undertaken by research assistants/midwives.

6.3.1. Women:

Eligible women will be initially identified and approached via a member of the clinical care team at the woman's hospital booking appointment who will introduce the study. If

permission to consider the study has been granted, they will notify the research assistant/midwife to discuss the study further. Written and verbal information (available in local languages) will be supplied and potential participants will be given time to consider participation. The woman will be encouraged to discuss with family/others (if accompanying her) and provided additional opportunities to ask questions. She will be informed that her participation is voluntary and a decision not to take part in the research will have no impact on her current or future healthcare provision. Women will be given the opportunity to confirm participation at the booking visit should they wish and provided with the consent form to sign. Others will be given the opportunity to confirm participation at their next antenatal clinic appointment, where consent form completion will take place. Women will be able to withdraw up until 1 week after taking part in the interviews.

6.3.2. Health workers (midwives, nurses, obstetricians, and support staff) and other hospital staff, including managers and administrators:

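### The protocol does not settle which clinic Phase 1 (control) women attend in months 4-7, and it provides no way to identify controls who move to the specialised clinic

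*Protocol*

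**What the plan says.** Section 5.4.1 is headed "Pre-implementation - control phase; months 1-7". It says that women recruited in this phase receive existing care and complete questionnaires at the beginning and towards the end of pregnancy. Section 5.3 allows two months for control recruitment, before the new service is introduced, and expects about 20 women. It does not say which two months.

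Section 5.4.2 sets Phase 2 at months 4-12 and adds: "The intervention will be implemented in the study site in month 4".

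Section 6.3 deals with the change of clinic: "The current antenatal clinic running throughout Phase 1 will be superseded with the specialised antenatal clinic in Phase 2 of the study period". The next sentence begins: "Both will be provided for all women attending antenatal services at the study site who have experienced a previous stillbirth", and it applies whether or not the woman takes part in the study.

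Section 5.2 reports that such women "book for antenatal care between 18-35 weeks gestation (median 26 weeks"). Section 7 collects clinical data, including antenatal visits and scans, at recruitment and at birth. Section 9.1.3 centres the quantitative analysis on confidence intervals for control-versus-intervention differences and on variances for the full trial.

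**The concern.** In months 4-7 the current clinic cannot both run to the end of Phase 1 and be replaced for all eligible women by a clinic that opened in month 4. The protocol gives no transition rule for women who booked under usual care and are still pregnant at launch.

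If such women move to the new clinic, their late questionnaire, visit counts, interviews and birth data reflect a mixture of the two services. Differences between cohorts would tend to shrink, and the usual-care means, SDs and resource counts carried into the full trial would not describe usual care. Section 5.1 argues that "individual randomisation would be undesirable due to the risk of contamination between the trial arms", so the same risk deserves handling in the feasibility comparison. The study is also meant to test whether a stepped-wedge approach is feasible, and pregnancies that span the switch are a central question for that design.

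**Working it through.** **Inputs from the protocol.** Phase 1 is months 1-7 (5.4.1). Launch is in month 4 (5.4.2). Control recruitment lasts two months, about 20 women (5.3). Booking is at 18-35 weeks, median 26 (5.2).

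**Assumptions, because the protocol does not state them.** Control recruitment is in months 1-2 (months 2-3 as the alternative), uniform over time. Launch is at the start of month 4 (3.0 months elapsed) or its end (4.0 months elapsed). Birth is at 37-40 weeks. The late questionnaire is at 36 weeks. One month is 4.345 weeks. Booking gestation takes one of three shapes on 18-35 weeks: uniform, split-uniform with median 26, or triangular with mode 26.

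**Step 1: reproduce the Phase 1 window.** Last control birth = end of recruitment + (40 − 18)/4.345 = 2 + 5.06 = 7.06 months. This matches months 1-7, so recruitment in months 1-2 with follow-up to birth is a plausible reading. It also means that months 4-7 are control follow-up.

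**Step 2: a woman booking at the median.** Gestation at launch = 26 + (launch − booking time) × 4.345.
- Booked on the first day of month 1, launch at start of month 4: 26 + 3 × 4.345 = 39.0 weeks.
- Booked at the end of month 2, same launch: 26 + 1 × 4.345 = 30.3 weeks.
- Booked at the end of month 2, launch at end of month 4: 26 + 2 × 4.345 = 34.7 weeks.

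Late bookers behave differently. A woman booking at 35 weeks at the end of month 2 (week 8.7) reaches 39 weeks at week 12.7, just before a launch at week 13.0.

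**Step 3: share of controls affected.** By simulation, a control counts as still pregnant if booking time + (birth week − booking week)/4.345 exceeds the launch time. The 36-week column uses 36 in place of the birth week. Ranges run over the three booking shapes and, for pregnancy, over birth at 37-40 weeks.

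| Recruitment | Launch | Still pregnant at launch | 36 weeks falls after launch |
|---|---|---|---|
| Months 1-2 | Start of month 4 | 61-87% | 55-59% |
| Months 1-2 | End of month 4 | 30-56% | 23-31% |
| Months 2-3 | Start of month 4 | 85-99% | 80-89% |
| Months 2-3 | End of month 4 | 61-87% | 55-59% |

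Of 20 controls recruited in months 1-2, 61-87% is about 12-17 women and 30-56% is about 6-11.

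**Step 4: could the phases simply be separated?** Without overlap, launch could not come before about 7.06 months. Two further months of recruitment and 22 weeks to the last birth give 7.06 + 7.06 = 14.1 months, beyond the 12-month study. Some overlap is built into the timetable, so it has to be identified and reported.

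**The case against.** The strongest reply is that the text is ambiguous and does not establish contamination. Section 5.4.1 promises existing care to control-phase women, section 6.3 keeps the current clinic going through Phase 1, and no sentence dates its closure. Section 5.4.2 recruits women booking in months 4 and 5, which would fit two clinics running side by side with cohorts defined by booking date. This stands in part. A reader might infer that most controls are in fact exposed, but the documents do not support that as a fact. They support a contradiction and a possible share, because the replacement of the clinic and its provision to all women weigh against the parallel reading without settling it.

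The figures also depend on dates that the protocol does not give. With recruitment in months 1-2 and launch at the end of month 4, fewer than a third of 36-week questionnaires fall after launch. A woman still pregnant at launch may also give birth before attending the new clinic. Both points stand, and the shares are therefore conditional and upper bounds.

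Two supporting signs are weak. Section 5.4.1 asks control interviews to capture experiences "including impacts of the intervention (study months 1-7 of Phase 1"), but this may be wording carried over from Phase 2. The month-2 item "Specialist antenatal clinical care staff will attend a training workshop" does not show that those staff treat controls.

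Finally, this is a feasibility study. Its key outcomes are recruitment and retention (section 7), progression rests on recruitment targets and 75% retention (9.1.1), and with about 20 women an SD already has a 95% interval of roughly −24% to +46%. That limits the consequences, but it does not remove the problem for the analyses named in 9.1.3. A later analysis plan could not repair it without data on the clinic attended. The intervention log (8.3.1) records contacts to measure uptake, but the protocol does not say that it covers Phase 1 women.

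**Conclusion.** The point holds as an unreconciled conflict between sections 5.4.1, 5.4.2 and 6.3 for months 4-7, with no stated means of identifying controls who cross over. The conflict is evident from the text and needs no simulation.

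Its possible size is substantial under every timetable examined: from 30% of controls still pregnant at launch in the most favourable case to 99% in the least. These figures rest on the assumed recruitment months, launch day, booking distribution and birth gestation, and they bound exposure from above. What is at risk is the cohort comparison, the variance estimates, the description of usual care and the assessment of the stepped-wedge approach. The recruitment and retention criteria are little affected. A reader might also infer that the full trial will inherit a missing transition period. The protocol does not support this, because section 4.2.2 leaves the full design still to be defined.

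**What to change.** 1. Reconcile sections 5.4.1, 5.4.2 and 6.3 on which clinic Phase 1 women attend from month 4. State the control recruitment months and the launch date.
2. Record the clinic attended at each antenatal visit for every participant in both phases.
3. Keep the late-pregnancy questionnaire at its planned gestation. Bringing it forward to before launch would confound cohort with gestation.
4. Report the cohort comparison and SDs for all Phase 1 women and, separately, by whether they attended the specialised clinic. Say that the unexposed subgroup is small and weighted to late bookers. Do not restrict the control cohort to that subgroup, since this would introduce selection.
5. Use the observed crossover to judge whether the stepped-wedge design needs a transition period.

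The cost is protocol wording and one visit-level data field, with no extra participants. The downside is that the subgroups will be small and their estimates imprecise. The timing of the staff training workshop need not change on this account.

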8.4. Psychological assessments

Women participants will complete the psychological assessment questionnaires at the time of booking and towards the end of their pregnancy:

8.5. Health economics

Data will be captured to identify the key resources associated with the intervention, including:

Human resources (direct) – the intervention log as described above will be used to identify person (antenatal clinical care staff) time spent performing all aspects of the intervention, including attending training and meetings.

Indirect resources – as part of the staff experience questionnaire, clinic staff will be asked about their perceived impact of the intervention on human and other resources and any additional equipment purchased in order to deliver the intervention.

Antenatal visits and out of pocket expenses – women will be asked in the questionnaire survey to report all antenatal visits and any interventions (e.g. scans) and about any out of pocket expenses incurred related to the intervention e.g. travel costs for attending additional specialist antenatal classes.

9) DATA ANALYSIS AND STATISTICAL CONSIDERATIONS

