- Women booking at the study site will be recruited during months 4 and 5 to explore experiences of attending the specialised antenatal clinic, worries in pregnancy and preparation for pregnancy and asked to complete questionnaires, at the beginning and towards the end of their pregnancy. A sub-sample of women will also be invited to attend focus group interviews or individual interviews, whichever they prefer, towards the end of their pregnancy to capture pregnancy experiences, including impacts of the intervention (study months 4-12).
- Monthly meetings (attended by the specialist antenatal clinical care staff, research team facilitator, hospital staff including managers and administrators) to share experiences and develop further strategies to improve clinical care practice and outcomes for women will be planned (study months 4-12).
- Health workers (midwives, nurses, obstetricians, and support staff), and other
 hospital staff, including managers and administrators, directly involved in the
 intervention will be asked to compete a staff experience questionnaire and offered
 the opportunity to attend a focus group interviews at the end of Phase 2 (study
 month 12).

6) STUDY PARTICIPANTS

6.1 Inclusion Criteria:

Pregnant women booking at the study site for antenatal care (during Phases 1 and
 with subsequent pregnancy following stillbirth (baby born dead at 28 weeks

gestation or more, with a birth weight of 1000grams or more or a body length of 35cm or more (WHO, 2019))

OR

Health workers (midwives, nurses, obstetricians, and support staff), and other hospital staff, including managers and administrators directly involved in the study intervention or who provide care of services to pregnant women at the study site.

• 18 years or over, at the time of recruitment (women).

6.2 Exclusion Criteria:

• Unable to give consent (women)

6.3 Recruitment:

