8.3.1. Uptake and additional impacts of the intervention on the practice and environment of care will be captured by:

An intervention log completed by specialist antenatal clinical care staff will summarise study related activities, to determine what was done, when and by whom. This will include training, meetings, adminstration, data for additional contacts including number of contacts, time spent, mode of support (additional clinic apointment or telephone call) with women to determine uptake of the support component of the intervention.

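### Direct staff resource is limited to clinic staff time, although research team members support launch and delivery, so the resource needed may be understated

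*Protocol*

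**What the plan says.** Section 8.5 (Health economics) sets the counting rule for direct human resources: "the intervention log as described above will be used to identify person (antenatal clinical care staff) time spent performing all aspects of the intervention". It adds that time in training and meetings counts. The bracket limits whose time is counted.

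The source is the log in section 8.3.1: "An intervention log completed by specialist antenatal clinical care staff will summarise study related activities, to determine what was done, when and by whom". The same staff fill it in. Section 5.4.1 says who they are: "an obstetrician and two midwives and one support worker with an interest in this topic will be required".

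Section 5.4.2 (Phase 2) describes who takes part in delivery:

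- **Launch, month 4:** "The specialist antenatal clinical care staff will initiate this with support from a research team facilitator, research assistants/midwives, and hospital staff", the last group including managers and administrators.
- **Delivery:** specialist care, psychosocial support and birth preparation "will be delivered by the specialist antenatal clinical care staff, with support from the research team facilitator (study months 4-12".
- **Meetings, months 4 to 12:** "Monthly meetings (attended by the specialist antenatal clinical care staff, research team facilitator, hospital staff including managers and administrators".

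Section 7 lists as an outcome the human and healthcare resources that go with delivering the intervention, without restriction to clinic staff. Section 4.2.2 aims to find out whether an economic evaluation is feasible, by exploring the main resources and how they can be captured reliably.

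**The concern.** The protocol names the facilitator as an input to delivery for the whole intervention phase, but the direct resource measure leaves that input out. If some of the facilitator's work is service rather than research, the count of staff time needed to run the clinic will be too low.

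Two aims are exposed. The first is the economic objective in 4.2.2, which is about capture. A capture method that skips a named contributor falls short of it even though no cost is to be estimated. The second is the assessment of implementation in 4.2.1. Section 5.1 foresees a stepped-wedge trial in which the intervention is rolled out to clusters in phases. Planning that trial requires knowing whether four clinic staff delivered the service themselves or needed regular outside help. Hours not recorded at the time cannot be reliably reconstructed at analysis.

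**Working it through.** The protocol gives no staff hours, costs or resource totals, so there is no figure to reproduce. The check sets the delivery text in 5.4.2 against the measurement text in 8.3.1 and 8.5.

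| Contributor | Role in 5.4.2 | Period | Direct time counted under 8.5? |
|---|---|---|---|
| Specialist clinic staff (1 obstetrician, 2 midwives, 1 support worker) | Launch, delivery, meetings | Months 4–12 | Yes |
| Research team facilitator | Support to launch and delivery, meetings | Months 4–12 | No |
| Research assistants/midwives | Support to launch | Month 4 | No |
| Managers and administrators | Support to launch, meetings | Month 4; meetings in months 4–12 | No |

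The monthly meeting shows the effect most plainly. The clinic staff's time at it counts, because 8.5 includes meetings. The time of the facilitator, managers and administrators at the same meeting does not.

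Four pieces of text might close the gap. Taken in turn:

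1. **The log records who carried out each activity (8.3.1).** This could show that the facilitator was involved. But time spent is listed there among the data on additional contacts with women, and 8.5 then draws time from the log for clinic staff only.
2. **The list in 8.5 is introduced as non-exhaustive.** That permits further capture but plans none.
3. **The staff questionnaire (8.5, indirect resources).** It asks clinic staff how they perceive the impact on human and other resources. A perception reported by one group does not measure another group's hours.
4. **The outcome in section 7 is worded broadly.** This makes the restriction in 8.5 narrower than the outcome it is meant to serve.

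None of the four records the missing hours.

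**Direction.** Let c be clinic staff delivery hours and e the delivery hours of others. The planned count is c, the full count is c + e, and the share missed is e / (c + e). This is zero if e = 0 and positive otherwise, so the omission can only lower the count.

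**Size.** Neither c nor e is in the protocol. For illustration only, assume each of the four clinic staff gives 4 h a week, so c = 4 × 4 = 16 h:

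- with e = 2 h a week, the share missed is 2 / (16 + 2) = 0.11
- with e = 8 h a week, the share missed is 8 / (16 + 8) = 0.33

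Only the headcount of four is documented. Every hour figure is assumed, so the range shows how the formula behaves and is not an estimate for this study.

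**The case against.** The strongest reply is that this is an exploratory resource exercise in a feasibility study. Section 4.2.2 asks which resources matter and how to capture them; it plans no cost or resource total. Learning whose time should be logged in a full trial is arguably one of the things the study is for. If facilitation belongs to the research, leaving it out of service time is a defensible costing choice. Dependence on the facilitator could also emerge from the interviews and questionnaires, since section 9.1.2 draws on the views of delivery staff and others involved in care.

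Much of this stands, and it limits the point. A reader might infer any of three stronger conclusions, and the protocol supports none of them:

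- **That resource need is understated and deliverability overstated, as established fact.** The protocol gives no facilitator hours. It does not split that time into service and research, and it does not say whether a facilitator would be present in a full trial or in routine use.
- **That research assistants/midwives support delivery through months 4 to 12.** Section 5.4.2 names them in a supporting role only at the month 4 launch. Support throughout is stated for the facilitator alone.
- **That the decision on a full trial is compromised.** The criteria in 9.1.1 are recruitment to target and 75% retention, with 60% as the lower bound for reconsideration. Resource data do not enter them.

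The reply does not remove the core. Excluding research time is defensible only if it is identified and the exclusion is stated, and 8.5 does neither. Interviews may show that help was given, but they will not give the hours. If the study is meant to learn whose time needs logging, it has to log more than one group's.

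**Conclusion.** The point holds as a risk of known direction and unknown size. Section 8.5 restricts direct human resource to clinic staff, while 5.4.2 names a facilitator who supports delivery and attends meetings through months 4 to 12, and others who help at launch or attend meetings. The direct staff resource needed to deliver the clinic may therefore be understated, by an amount the documents do not allow anyone to compute. The study will also have no measure separating what clinic staff delivered alone from what relied on the research team.

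This rests on reading the bracket in 8.5 as the counting rule, and on at least part of the supporting time being service delivery. If all of it were research, nothing would be missing from the service count, but the protocol would still need to say so. The resource and implementation objectives are affected; the recruitment and retention criteria are not. It should be changed, because the data are lost if not collected at the time.

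**What to change.** In 8.3.1 and 8.5, extend the log and the direct human resource measure to the facilitator and any other supporting staff: research assistants/midwives at launch, and managers and administrators at launch and at meetings. Add two fields to each entry, a staff role and a code for service delivery versus research (such as consent, questionnaires and interviews). Exclude only entries coded as research, and say so.

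Report delivery time with and without research team input. State in the feasibility conclusions which components relied on that input. If the team prefers to leave the facilitator's time out, 8.5 should give the reason.

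The cost is one role column and one activity code in an existing log, and a few minutes of extra logging a week. The resource figure may also look less favourable. No change is needed to the sample size, the participant procedures or the criteria in 9.1.1.
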